***Please add a Study Contact**

[name], MA
[name], PhD

The Study Contact(s) will receive all important system notifications along with the Principal Investigator. (e.g. The project contact(s) are typically either the Study Coordinator or the Principal Investigator themselves).

**VASDHS IRB
Human Subjects Protocol
v20190121**

Section 1 - Preliminaries

Principal Investigator:

[name]

Protocol Title:

Cognitive Rehabilitation for Homeless OEF/OIF/OND Veterans

IRB Protocol Number:

H150168

Protocol Nickname:

CogSMART Homeless

Form Template Version:

v20150115

Date Prepared:

02/02/2023

Please be advised that this protocol application form has changed as a result of the 2018 Common Rule. There are new questions and sections, and you may be required to provide additional information to previous sections.

1a) Is this study considered human research?

- Yes
- No
- I don't know

1b) Please select:

Was this study initially approved prior to January 21, 2019?

Yes No

Were you instructed to convert to the 2018 Common Rule Requirements?

Yes No

Section 2 - Research Subjects

2a) What is the total planned number of VA-consented subjects?

Include the total number of subjects who will prospectively agree to participate in the study (e.g., documented consent, oral consent, or other).

98

2b) What is the total number of VA subjects who WILL NOT be consented?

Include the total number of subjects that will be included without consent (e.g., chart review). *Note: Data about people are still considered "human subjects" by the IRB, so even if you do not intend to contact the patients whose charts you will review, you still should enter the number of charts as your "planned subjects."*

0

Section 2.1 Consented Subject Groups

2.1) For each of the subject categories listed below, indicate whether or not these subject groups will participate in the study:

2.1a) Children under the age of 18

Note: If neonates or children will be involved in this study, certification by the Medical Center Director will be required. Only minimal risk research may be performed with children. Only non-invasive monitoring and/or prospective observational and retrospective record review studies that are minimal risk can be conducted in VA involving neonates.

Yes No

2.1b) Pregnant women

Yes No

2.1c) Individuals with cognitive/decisional impairment

Yes No

2.1d) Non-English-speaking individuals

Yes No

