The subject population in this study will be 50 male and female O/O/O Veterans with mental health conditions and cognitive impairment served by the Aspire Center. It is anticipated that we will need to enroll and test 200 participants to end up with 98 who have cognitive impairment. We anticipate the top four mental health conditions to be PTSD, depression, history of substance use disorder, and history of TBI. Our inclusion criteria were selected in order to increase generalizability to other treatment-seeking homeless O/O/O Veterans with cognitive impairment. Participants will be men and women of any race/ethnicity, aged 18-55 years (which will represent the vast majority of O/O/O Veterans, but not introduce age-related dementing disorders as a confound). Complete inclusion/exclusion criteria are as follows:

Inclusion Criteria:

- 1) Male or female, any race/ethnicity, and age 18-55
- 2) Meets criteria for Aspire Center program entry
 - a) O/O/O Veteran
 - b) presence of at least one DSM-V mental health condition
 - c) does not meet criteria for substance use disorder for 28 days prior to admission
 - d) homeless or unstably housed (per HEARTH Act definition; HUD, 2011b)
 - e) not a sex offender or violent offender
 - f) capable of performing activities of daily living and transfers
 - g) not judged by a clinician to be at current risk to self or others
- 3) Has cognitive impairment in at least one cognitive domain (i.e., T-score < 40)
- 4) Able to speak and read English
- 5) Capable of and willing to provide signed informed consent

Exclusion Criteria:

None

Although it is recognized that the effects of chronic alcohol abuse can last longer than 28 days, the number of individuals in the study with recent alcohol abuse should be equally allocated across the two treatment groups by virtue of the power of randomization. In the unlikely event in a study this size that the treatment groups differ in this regard, alcohol history may be used as a covariate in the analyses.

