All participants will provide voluntary informed consent (we will not enroll participants who require surrogate consent). All potential participants who meet the inclusion and exclusion criteria above will be invited to participate; we anticipate that about 50% of the Aspire Center residents will meet these criteria and choose to participate, based on our prior research experience with homeless individuals (Vella et al., 2014). Those who enroll but turn out not to have cognitive impairment will end their research participation and will not participate in the randomized controlled trial; these participants will be replaced until the target enrollment of 98 participants is reached. Potential participants will meet with a project staff member, who will describe the study and answer any questions. In all cases, fully informed consent will be obtained. [name] will be directly available to answer any questions raised by a potential participant. A copy of the consent form, which includes a description of the study, will be provided to all subjects. The study population is at risk for diminished capacity to consent to research by virtue of their expected cognitive impairment, so participants will be assessed for capacity to consent for this study with a post-consent quiz, which will include questions about the purpose of the study, types of assessments, number of groups, voluntariness, and the ability to withdraw at any time without penalty. Potential participants will be given three chances to answer each question correctly, with the correct information provided in the event the individual answers incorrectly. We have used this procedure in prior studies to ensure decisional capacity. Four out of the five questions are open-ended in order to reduce the chance that the consenter could inadvertently reveal the right answer.

Inclusion of Women, Ethnic Minorities, and Children

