The sole recruitment source for this study will be the VA Aspire Center, a 40-bed Residential Rehabilitation Treatment Program serving homeless O/O/O Veterans with mental health conditions such as PTSD, depression, and TBI. A rate of accrual of 10 participants enrolled per quarter during the recruitment period (last three quarters of Year 1; Year 2; first quarter of Year 3) would be required to support our targeted accrual. The average length of stay is 3-6 months, meaning that between 80 and 160 participants per year would be eligible for the study. We aim to enroll 30 participants in the last three quarters of Year 1, 40 in Year 2, and 10 in the first quarter of Year 3, making our enrollment goals feasible. Our research team has held several planning meetings with the Aspire Center team and has identified a plan for successful recruitment that maximizes the possibility that participants will be enrolled while being minimally disruptive to Aspire Center operations. To facilitate recruitment, our PI and study staff will be highly visible at the Aspire Center and will coordinate with program intake staff (please see Letter of Support from [name], LCSW, Chief of the Aspire Center). Individuals who meet the inclusion criteria outlined above will then be approached for potential participation in the study and, if interested, will complete the consenting process and the baseline assessment.

Retention

During the trial, assessments will be administered at baseline, 5 weeks, 10 weeks, and 15 weeks, and brief monthly follow-up phone calls will assess housing and employment/education status for one year following program discharge. Participants will be compensated for their time spent in assessments (\$25 per assessment X 4 assessments = \$100 maximum total compensation) as a way to enhance retention. Based on prior studies of Veterans with PTSD and/or TBI, we expect about 20% attrition, for a final sample size of 78 (39 per group). Attrition may be even lower, given that all participants will be residing on-site. Monthly follow-up assessment of housing/employment status will be brief and not burdensome to participants.

Procedure

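### The enrolment counts contradict each other: power rests on 98 randomised, but the form gives 98 consented, Section 9 opens with 50, and the accrual plan adds up to 80

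*Combined protocol and SAP*

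**What the plan says.** All of the following is current text in the combined protocol and SAP.

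- **Section 2a** asks "What is the total planned number of VA-consented subjects" and the answer is 98. The form's instruction counts everyone who prospectively agrees to take part, so people who later fail screening are included.
- **Section 9, first sentence:** "The subject population in this study will be 50 male and female O/O/O Veterans". The sentence goes on to describe them as having cognitive impairment.
- **Section 9, next sentence:** "It is anticipated that we will need to enroll and test 200 participants to end up with 98 who have cognitive impairment".
- **Section 9, replacement rule** for enrollees found not to be impaired: "these participants will be replaced until the target enrollment of 98 participants is reached".
- **Section 9, expected participation:** "we anticipate that about 50% of the Aspire Center residents will meet these criteria and choose to participate".
- **Section 9, Recruitment:** a rate of 10 enrolled per quarter "would be required to support our targeted accrual", and "We aim to enroll 30 participants in the last three quarters of Year 1, 40 in Year 2, and 10 in the first quarter"; that last quarter falls in Year 3. Resident turnover is given as "meaning that between 80 and 160 participants per year would be eligible for the study".
- **Section 9, Retention, and the H1a and H1b power analyses:** 20% attrition and a final sample of 78, 39 per group. H1a names 98 as the target.
- **Section 10:** a population of 98, with about half of consented participants expected to lack impairment and to stop after baseline.

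**The concern.** Consent comes before testing, and testing decides who is randomised. A count of people consented and a count of people randomised therefore differ by a factor of about two in this trial, and the plan does not keep them apart. Section 9 uses *enroll* for the 200 who are tested and again for the 98 who remain after testing. The accrual schedule uses the same word without saying which it means.

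Two of the conflicting counts are operational. Section 2a is the declared consent total, and the accrual schedule is the only recruitment timetable in the document. If either is followed as written, the trial ends below the sample on which its power rests. The replacement rule cannot deliver 98 impaired participants within 98 consents unless nobody fails screening, and the plan itself expects about half to fail.

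**Working it through.** **1. Reproduce the plan's own figures.**
- Attrition: 98 × (1 − 0.20) = 78.4, so 78, or 39 per group. This agrees with Retention and both power analyses.
- H1b: two-sample t-test, 39 + 39, effect size 0.64, two-sided alpha 0.05: power 0.797. This matches the stated 0.80.
- H1a: the Analytic Plan names a Bonferroni adjustment but gives no alpha. I assume two-sided 0.025 (two co-primary outcomes) or 0.0167 (three outcomes). At 39 + 39 and effect size 0.72, power is 0.812 or 0.766, in line with the stated 0.80. The RMASS program was not rerun. With the plan's correlation of 0.5 between time points, an end-minus-baseline contrast has variance 2 × (1 − 0.5) = 1, so the t-test is a reasonable proxy.

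**2. Compare the counts.**
- Impairment yield: 98/200 = 0.49, in agreement with Section 10's half.
- Section 2a: 98 × 0.5 = 49 randomised; 49 × 0.8 = 39 completers in total. The plan needs 39 *per group*.
- Section 9 opening: 50 × 0.8 = 40 completers; 98 − 50 = 48 short.
- Accrual: 30 + 40 + 10 = 80, and 10 × (3 + 4 + 1) quarters = 80. If these are randomised, 98 − 80 = 18 short, and 80 × 0.8 = 64 completers. Finishing with 78 of 80 would need attrition of 2/80 = 2.5%, not 20%. If they are consented, 200 − 80 = 120 short.

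**3. Power under each count.** Noncentral t with df = n1 + n2 − 2 and noncentrality d × √(n1·n2/(n1 + n2)). For H1a (d = 0.72) the noncentrality is 0.72 × √19.5 = 3.18 for 39 + 39, 0.72 × √16 = 2.88 for 32 + 32, 0.72 × √10 = 2.28 for 20 + 20, and 0.72 × √(380/39) = 2.25 for 20 + 19.

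| Count followed | Completers | H1a, alpha 0.025 | H1a, alpha 0.0167 | H1b (d = 0.64), alpha 0.05 |
|---|---|---|---|---|
| 98 randomised | 39 + 39 | 0.81 | 0.77 | 0.80 |
| 80 randomised | 32 + 32 | 0.72 | 0.66 | 0.71 |
| 50 randomised | 20 + 20 | 0.48 | 0.42 | 0.51 |
| 98 consented | 20 + 19 | 0.47 | 0.41 | 0.49 |

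With 32 + 32, the H1a effect detectable at 0.80 power is 0.79 (alpha 0.025) or 0.83 (0.0167). At unadjusted 0.05, 32 + 32 would give 0.81 for d = 0.72, but the plan says its H1a power already allows for the Type I correction.

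**4. Rate needed over the stated 8 quarters.** 98/8 = 12.25 randomised, or 200/8 = 25 consented, per quarter, against the planned 10.

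**5. Feasibility on the plan's own turnover.** Forty beds with stays of 3 to 6 months give 40 × 2 to 40 × 4 = 80 to 160 a year. The number called eligible therefore equals the whole resident turnover. Over 8 quarters that is 160 to 320 residents. At the expected 50% participation it is 80 to 160. If that 50% counts consents, it is below 200. If it already includes impairment, it is 80 to 160 randomised, a range that contains 98.

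**The case against.** The strongest counter-argument is that there are two competing sets of numbers, not one sound target with three stray counts. Section 2a (98 consented), Section 10 (98, about half not impaired) and the opening of Section 9 (50 impaired) fit one another, since 98 × 0.5 = 49. Section 10's population sentence also leaves out cognitive impairment, although its criteria include it. This may explain where the 50 came from. The documents do not say so, however, and the set contradicts the sentence giving 200 tested for 98 impaired, the replacement rule, and the H1a target of 98. If it were the true plan, the stated power would be wrong.

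Second, the accrual schedule is a projection and the replacement rule is what stops enrolment. If the schedule counts randomised people, the missing 18 need 18/10 = 1.8, about two more quarters, within a study estimated at 5 years. That is a fair limit on the consequence. If it counts consented people, the missing 120 need 120/10 = 12 more quarters. With the first 8 that makes 20 quarters of recruitment, as long as the whole estimated study.

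Third, the power losses are scenarios. The alphas are assumed, and the t-test counts completers only, whereas the mixed model uses everyone with at least one post-baseline visit. This stands, and the case for correcting the counts does not depend on those figures. Nor do the documents show that 98 is out of reach.

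**Conclusion.** The concern holds. Within current text, 98 consented, 50 impaired, 80 accrued, and 98 impaired from 200 tested cannot all be true. The intended target can be recovered: 98 randomised is the only figure that fits the testing yield, the replacement rule and the power analysis together, and the power statement is consistent with it. The inconsistency costs power only if Section 2a or the accrual schedule is followed as written. H1a power at 0.72 would then be about 0.47 (98 consents) or 0.72 (80 randomised), against 0.81 as planned. These values assume a t-test proxy, two-sided alpha 0.025, 20% attrition and a 50% screen-failure rate; at alpha 0.0167 they are 0.41, 0.66 and 0.77. This should be corrected, and confidence in the contradiction itself is high.

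**What to change.** Use one set of numbers and keep consented and randomised apart throughout.

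- **Section 2a:** enter about 200 consented. Allow for more if effort-test failures are not already inside the 98/200 = 49% yield; the documents do not say.
- **Section 9, opening:** replace 50 with 98 randomised.
- **Section 9, Recruitment:** restate accrual as at least 12.25 randomised, about 25 consented, per quarter over 8 quarters, or state a longer recruitment period that reaches 98.
- **Feasibility:** say whether the 80 to 160 a year are all residents or only eligible ones, and whether the 50% participation figure counts consents or already includes impairment.
- **If 80 is the real randomised target:** leave the schedule, align the other counts to it, and restate power on 64 completers. The detectable H1a effect is then about 0.79 to 0.83 under the alphas assumed here, and H1b power at 0.64 is about 0.71 at alpha 0.05.

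The cost is a text amendment to Sections 2a and 9. The randomised target of 98 does not rise. The declared consent total rises by 200 − 98 = 102, which the testing sentence in Section 9 already implies. If 80 is chosen, the cost is a less favourable power statement.

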- e) not a sex offender or violent offender
- f) capable of performing activities of daily living and transfers
- g) not judged by a clinician to be at current risk to self or others
- 3) Has cognitive impairment in at least one cognitive domain (i.e., T-score <40)
- 4) Able to speak and read English
- 5) Capable of and willing to provide signed informed consent

Exclusion Criteria:

None

We anticipate that about half of consented participants will NOT have cognitive impairment (criterion 3, above). Those participants will end their participation after completing the baseline assessment

Section 10.2 Pregnant Women

10.2a) Are pregnant women the focus of the research?

Yes No

10.2b) Provide the justification for including pregnant women and address any special risks, protections, and safeguards.

Although we are not targeting pregnant women specifically, there is no reason to exclude a pregnant woman who would like to participate in the study and meets the inclusion criteria.

Section 10.5 Individuals with Cognitive/Decisional Impairment

10.5) Provide the rationale and additional study procedures that will be required for including individuals with known cognitive impairment or institutionalized individuals. *Address Decisional Capacity Assessment and Surrogate Consent Sections 12.6 and 12.7.*

The trial is to study an intervention to improve cognition in Veterans with cognitive impairment.

Section 11 - Recruitment

11) Describe, step-by-step, the plans for recruitment of subjects (or selection of subjects as in record review). This description must include how, when, and where potential subjects are approached as well as procedures for identifying potential participants (through medical records, physician referral, third-party sources, etc.). Include how selection is equitable. Indicate if vulnerability to coercion may be present and if so plans to ensure voluntary participation.

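### The yearly supply of eligible Veterans is simply full bed turnover, so the unqualified statement that enrolment is feasible in eight quarters is not supported across the plan's own 3-6 month range of stay

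*Combined protocol and SAP*

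**What the plan says.** All of the supply argument is in Section 9 - Design and Methods.

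- **Source.** "The sole recruitment source for this study will be the VA Aspire Center, a 40-bed Residential Rehabilitation Treatment Program" (Recruitment).
- **Stay and supply.** "The average length of stay is 3-6 months", "meaning that between 80 and 160 participants per year would be eligible for the study" (Recruitment).
- **Window.** Three quarters of Year 1, all of Year 2 and one quarter of Year 3, at 10 enrolled per quarter. The paragraph ends this schedule with "making our enrollment goals feasible".
- **Share of residents.** In the paragraph on consent: "we anticipate that about 50% of the Aspire Center residents will meet these criteria and choose to participate". The next sentences say that people who enrol and prove unimpaired leave the study and are replaced until 98 is reached.
- **Testing yield.** In the subject-population paragraph: "It is anticipated that we will need to enroll and test 200 participants to end up with 98 who have cognitive impairment". Section 10 - Human Subjects agrees: "We anticipate that about half of consented participants will NOT have cognitive impairment".
- **Past recruitment.** Recruitment cites a 90% rate among sheltered homeless participants. It comes from the same earlier study that is cited for the 50%.

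Cognitive impairment is inclusion criterion 3 in both Section 9 and Section 10.

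**The concern.** The supply figure is described as a count of eligible people, but both of its ends can be produced from beds and length of stay alone. The plan itself expects only about half of residents to qualify and take part, and only about half of those who consent to be impaired. Neither proportion is visibly applied before the plan declares its goals feasible.

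What is at stake is the recruitment calendar. The plan needs 200 people tested and 98 randomised from a single unit within two years. If the pool is overstated, the window may be too short at the longer stays that the plan allows, and whoever funds or oversees the trial would not learn this from the text.

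**Working it through.** **Inputs.** 40 beds; mean stay 3-6 months; window 3 + 4 + 1 = 8 quarters = 2 years; 200 tested for 98 impaired, i.e. 98/200 = 49%; about 50% of residents qualifying and taking part; 90% past recruitment rate. All are from Section 9. Full occupancy is my assumption; it is also what the plan's figure implies.

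**Step 1: reproduce the plan's figure.** Admissions per year = beds x 12 / stay in months.

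- 6-month stay: 40 x 12/6 = 80
- 3-month stay: 40 x 12/3 = 160

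Both ends match exactly, so no filter of any kind is in the 80-160.

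**Step 2: admissions in the window.** 80 x 2 = 160 to 160 x 2 = 320.

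**Step 3: the 200 to be tested as a share of these.**

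- Admissions only: 200/320 = 62.5% to 200/160 = 125%
- Adding 40 residents present on the first day: 200/360 = 56% to 200/200 = 100%

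At the 6-month end, a 90% recruitment rate gives 0.90 x 160 = 144 tested, or 0.90 x 200 = 180 with the residents in place. Both are below 200.

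**Step 4: number randomised.** This depends on the share of residents who end up randomised:

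- A: the 50% already includes impairment, share 0.50
- B: 90% consent and 49% impaired, share 0.90 x 0.49 = 0.441
- C: the 50% is consent before impairment testing, share 0.50 x 0.49 = 0.245

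| | Randomised in 8 quarters (6- to 3-month stay) | With 40 in place at the start | Longest mean stay that gives 98 from admissions | Quarters to 98 (3- to 6-month stay) |
|---|---|---|---|---|
| A | 80-160 | 100-180 | 4.9 months | 4.9-9.8 |
| B | 71-141 | 88-159 | 4.3 months | 5.6-11.1 |
| C | 39-78 | 49-88 | 2.4 months | 10-20 |

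Randomised = admissions x share. Longest stay = 40 x 12 / (98 / share / 2): for A, 480/98 = 4.9; for B, 480/111.1 = 4.3; for C, 480/200 = 2.4. Quarters = 98 / (admissions per quarter x share), with 40 admissions per quarter at 3 months and 20 at 6 months.

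**Not included.** Lower occupancy would reduce every row. So would exclusions for failing the effort test, which the plan expects to be under 10%; at 10%, row C becomes 35-71.

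**The case against.** The strongest reply is that the target may well be reachable. The 50% refers to residents who meet the criteria and agree to take part, and impairment is one of those criteria, so multiplying by 49% again could count impairment twice. On reading A the window gives 80-160, and 100-180 with the residents already in place, which covers 98 at every stay from 3 to 6 months. The planned 40 per year also equals 50% of 80, so a cautious rate may have been applied to the low end without being stated. This stands to the extent that the documents do not settle the meaning of the 50%.

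It does not remove the point. The sentence after the 50% has people enrolling and only then being found unimpaired, which favours C. Taken exactly, reading A with 49% of those tested impaired needs 0.50/0.49 = 102% of residents tested. Both rates are stated as approximate, so the 2-point excess proves nothing alone, but A still needs close to universal consent, above the cited 90%. And whichever reading is meant, testing 200 at the 6-month end needs every resident, even counting those in place at the start.

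A reader might infer two stronger things:

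- **That the trial will randomise only 39-78.** That is reading C alone. On A and B, 98 is reachable at stays inside the plan's range.
- **That the stated .80 power is lost.** Power follows the number randomised and retained, not the calendar. Section 9 continues replacement until 98 is reached, and Section 4 allows 5 years for the whole study. Power falls below .80 on this account only if recruitment stops short of 98, which the plan does not propose.

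**Conclusion.** The supply figure is mislabelled: 80-160 per year is the unit's full turnover, not the number of eligible Veterans. The feasibility statement that rests on it holds for part of the 3-6 month range and not for the rest. From admissions alone, 98 in eight quarters needs a mean stay of at most about 4.9 months (A) or 4.3 months (B), and on C it is out of reach anywhere in the range. Put as time, 98 takes about 5-10, 6-11 or 10-20 quarters against the eight planned.

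These results assume full occupancy and steady turnover. Counting 40 residents at the start assumes that all can be approached; it rescues A throughout, B in part and C not at all. The separate fact that the accrual schedule sums to 30 + 40 + 10 = 80 rather than 98 or 200 is a different matter: correcting that total would leave the supply figure as it is.

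**What to change.** In Section 9, Recruitment:

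1. Describe 80-160 as admissions per year at full occupancy.
2. State whether the 50% in the consent paragraph includes cognitive impairment.
3. Give the consented and randomised numbers per year that follow from that answer.
4. Either restate the recruitment period needed for 200 tested and 98 randomised, or make the feasibility statement conditional on the mean stay and say which stay it needs.

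The 39-78 total, or its yearly equivalent of about 20-39, should not be written in as fact, because it would settle a question that only the study team can answer. The 5-year duration in Section 4 has room for some extension; 20 quarters, the far end of C, would use all of it.

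The cost is a less favourable feasibility statement and possibly a longer recruitment period. No procedure, outcome or analysis changes.
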